Study Week		W0	W2	W4	W8	W12	W16	W20	W24	W28	W32	W36	W40	W44	Any Week		
Study Day (Approximately)		1e	14	28	56	84	112	140	168	196	224	252	280	308	Any Day	28 ± 5 Days after Last Dose	
Visit Window (Days)			±3			±7											
Tanner Staging in patients ≥8 years old (see Section 9.4.6.3)	X																
Height	X	X						X				X		X	X		
Weight	X	X	X	X	X	X	X	X	X	X	X	X	X	X	X	X	
X-ray of wrist, hand, finger, and AP knee	X																
Uveitis evaluation ^h	X																
Dispense study drug ^l		X		X	X	X	X	X	X	X	X	X	X	X			
Investigational product returned and compliance assessed ^k			X	X	X	X	X	X	X	X	X	X	X	X	X	X	
Childhood Health Assessment Questionnaire ^l		X		X	X	X	X	X	X	X	X	X	X	X	X	X	
CHQ-PF50 ^h		X		X	X	X	X	X	X	X	X	X	X	X	X	X	
EQ-5D- Y ^l		X		X	X	X	X	X	X	X	X	X	X	X	X	X	
SPARCC Enthesitis Index ^{km}		X	X	X	X	X	X	X	X	X	X	X	X	X	X	X	
Morning stiffness		X	X	X	X	X	X	X	X	X	X	X	X	X	X	X	

Visit #	Screening		Open-Label Lead-in Period ^a				Double-Blind Randomized Withdrawal Period							Early Termination	Post-Treatment Follow-Up			
	V1	V1a	V5b baseline	V6	V7	V8	V9	V10	V11	V12	V13	V14	V15			V16	V17	
Study Week			W0	W2	W4	W8	W12	W16	W20	W24	W28	W32	W36	W40	W44		ETV ^c	V801 ^d
Study Day (Approximately)	-42 to -1		1 ^e	14	28	56	84	112	140	168	196	224	252	280	308		Any Day	28 ± 5 Days after Last Dose
Visit Window (Days)				±3				±7										
duration ^h																		
Pain Numeric Rating Scale ^h			X	X	X	X	X	X	X	X	X	X	X	X	X	X	X	X
Clinical sacroiliitis ^{im}			X	X	X	X	X	X	X	X	X	X	X	X	X	X	X	X
Back mobility ^{km} (Schober's test)			X	X	X	X	X	X	X	X	X	X	X	X	X	X	X	X
PAS ^h			X	X	X	X	X	X	X	X	X	X	X	X	X	X	X	X
Chest x-ray ^{no}	X																	
Administer PPD/Quantiferon [®] -TB Gold/T-SPOT [®] TB ^{pp}	X																	
Read PPD ^{pp}		X																
ECG ^{qg}	X																	
hsCRP	X		X	X	X	X	X	X	X	X	X	X	X	X	X	X	X	X
ESR ^{pf}			X	X	X	X	X	X	X	X	X	X	X	X	X	X	X	X
HLA-B27							X											
RF and ACPA	X																	
TSH	X																	
HIV/HCV ^{qs}	X																	
HBV (hBsAg, hBcAb, hBsAb)	X																	
HBV DNA ^{fl}	X						X			X			X		X	X	X	X

Visit #	Screening		Open-Label Lead-in Period ^a				Double-Blind Randomized Withdrawal Period							Early Termination	Post-Treatment Follow-Up		
	V1	V1a	V5b baseline	V6	V7	V8	V9	V10	V11	V12	V13	V14	V15			V16	V17
Study Week			W0	W2	W4	W8	W12	W16	W20	W24	W28	W32	W36	W40	W44		
Study Day (Approximately)	-42 to -1		1 ^e	14	28	56	84	112	140	168	196	224	252	280	308		28 ± 5 Days after Last Dose
Visit Window (Days)				±3			±7										
Serum pregnancy test ^f U	X																
Urine pregnancy test ^f U			X	X	X	X	X	X	X	X	X	X	X	X	X	X	X
Clinical chemistry [†] Y	X		X	X	X	X	X	X	X	X	X	X	X	X	X	X	X
eGFR			X														
Fasting lipid panel [‡] W			X				X				X				X		X
Lymphocyte subsets (T, B, NK, and T-cell subsets) [§] Z			X		X		X								X		X
Antipneumococcal IgG multianalyte Ab assay ^{**} Y			At relevant visits for prevaccination, 4 weeks post vaccination, and 12 weeks post vaccination based on the vaccination schedule of each patient														
Anti-tetanus toxoid IgG, anti-diphtheria toxoid, and anti-pertussis toxoid Ab assay ^{**} Y			At relevant visits for prevaccination, 4 weeks post vaccination, and 12 weeks post vaccination based on the vaccination schedule of each patient														
Gonadal hormone ^{**} Z			X				X								X		X
PK sample ^{††} aa			X	X	X	X	X	X	X	X	X	X	X	X	X	X	X

Abbreviations: ~~AP~~ = anteroposterior;

- ~~h~~ Semiannual wrist, hand, finger, and ~~AP~~ knee radiographs to monitor bone age and long bone growth. Imaging will be required until skeletal maturity is attained, and this should be determined by a qualified physician at the site. For patients already enrolled in Study JAHV at the time of this amendment, the x-ray procedures will be optional. For these ongoing patients that consent to the x-ray procedures, x-rays must be completed within 30 days from time of consent/assent and every 6 months \pm 30 days thereafter.
- ~~hi~~ All patients with active uveitis must be excluded at screening. ~~If investigators consider it necessary, evaluation can be added at any visit.~~ Signs and symptoms of active uveitis should be monitored. Patients with ERA and JPsA should have a uveitis evaluation at W12 (V9), W44 (V17), ETV and V801. may have a higher risk of active uveitis so mandatory evaluation is required at W12 (V9), W44 (V17), ETV, and V801.
- ~~j~~ Study drug should not be dispensed before review of the Trial Manager report.
- ~~jk~~ Patients will return all investigational products for drug accountability.
- ~~jl~~ Patient-reported questionnaires will be administered via an on-site eCOA device or paper and is recommended to be completed prior to any clinical examinations.
- ~~km~~ Only for patients with enthesitis-related juvenile idiopathic arthritis (ERA) or juvenile psoriatic arthritis (JPsA).
- ~~kn~~ Only for patients with JPsA.
- ~~no~~ Only for patients with a history of active or latent TB with documented evidence of appropriate treatment and patients with a positive or repeated not-negative TB test(s) (either PPD, QuantiFERON[®]-TB Gold, and/or T-SPOT[®]). A chest x-ray (posterior-anterior view) will be performed at screening unless one has been performed within the past 6 months and the x-ray and reports are available for review.
- ~~np~~ TB tests include PPD, QuantiFERON[®]-TB Gold, and T SPOT[®]. In countries where the QuantiFERON-TB Gold test or T-SPOT is available, either test may be used instead of the PPD TB test. The QuantiFERON-TB Gold test may be performed locally or centrally; the T-SPOT must be performed locally. PPD tests must be read 48 to 72 hours after screening. (Note: Exception: Patients with a history of active or latent TB who have documented evidence of appropriate treatment, have no history of re-exposure since their treatment was completed, and have a screening chest x-ray with no evidence of active TB may be enrolled if other entry criteria are met. Such patients would not be required to undergo the protocol-specific TB testing but must have a chest x-ray at screening.)
- ~~eq~~ An ECG performed within 1 year prior to screening may be used.
- ~~pr~~ Performed locally. To be drawn prior to dosing early in the visit except for V6 and V7.
- ~~qs~~ For patients who are positive for HCV antibody, a follow-up test for HCV RNA is required. Patients with a positive HCV antibody will return to the site and have an HCV RNA sample drawn, which will be processed centrally. Results must be known prior to enrollment. Patients who are positive for HCV antibody and negative for HCV RNA may be enrolled.
- ~~rt~~ For patients who are positive for hBcAb, a follow-up test for HBV DNA is required. Patients with a positive hBcAb will return to the site and have an HBV DNA sample drawn, which will be processed centrally (for patients in Japan, it is acceptable for sites to draw HBV DNA samples with the test of Visit 1). Results must be known prior to enrollment. Any enrolled patient who is hBcAb positive, regardless of hBsAb status or level, must undergo HBV DNA testing per the schedule of events.
- ~~su~~ Pregnancy tests prior to first dose of investigational product for females \geq 10 years old of age (<10 years at investigator discretion) if menarche reached or if there is reason to believe the patient is sexually active. Pregnancy test results from Visit 5 must be known prior to first dose of investigational product.
- ~~tv~~ Clinical chemistry will include eGFR (calculated by Bedside Schwartz 2009 formula or the Japanese Society for Pediatric Nephrology formula for patients in Japan).

⚡Fasting lipid profile: Patients should not eat or drink anything except water for 4-12 hours depending on weight and age as specified below. If a patient attends these visits in a nonfasting state, this will not be considered a protocol violation. Recommended fasting times by age and weight are as follows:

- Patients ≥ 12 years: fast for 12 hours prior to laboratory test
- Patients 8 to <12 years and weighing >50 kg: fast for 12 hours prior to laboratory test
- Patients 8 to <12 years and weighing ≤ 50 kg: fast for 8 hours prior to laboratory test
- Children <8 years and weighing 25 to ≤ 50 kg: fast for 8 hours prior to laboratory test
- Children <8 years and weighing 10 to <25 kg: fast for 6 hours prior to laboratory test
- Children <8 years and weighing <10 kg: fast for 4 hours prior to laboratory test

⚡ Patients in the age cohort of age 2 to ≤ 7 years will not have flow cytometry testing due to blood volume limitations.

⚡ If patients are eligible for vaccination with tetanus, diphtheria, and pertussis (tDaP) and/or pneumococcal conjugate vaccine according to local recommended schedule of vaccination, IgG titers for eligible vaccine will be evaluated at prevaccination, 4 weeks post vaccination, and 12 weeks post vaccination.

⚡ Estradiol (for females) or testosterone (for males) will be collected for the assessment of pubertal development in patients aged 8 to <18 years.

⚡ PK samples will be collected as described in Sections 9.5.2 and 9.5.3.

NOTE: Due to blood volume restrictions, some laboratory tests may not be collected. Laboratory samples are recommended to be collected as described in the sponsor-provided weight-based prioritization chart in [Appendix 6](#).

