7.4. Dosage Modification

The baricitinib dose for an individual patient will not change during the course of this study. However, the baricitinib dose for an age-based cohort may change based on the PK and safety profile of doses evaluated during the PK lead-in period. All patients who complete the PK lead-in period will enter the OLLI period on the dose they received at the start of the PK lead-in period. If the dose is modified for an age group after patients have already entered the OLLI period, they will be discontinued from the study and will be given the option to move to a separate OLE and receive the modified dose. Data from these patients will be censored from statistical analyses of efficacy endpoints in the present study.

The baricitinib dose for patients will be reduced by 50% in those who have renal impairment (defined as eGFR <60 mL/min/1.73 m²) at baseline. Patients receiving the 1-mg tablet who have renal impairment at baseline will be dose-reduced to 0.5-mg using the oral suspension.

Patients with eGFR <60 mL/min/1.73 m² are excluded from the safety/PK assessment period as described in Section 6.2.

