8.1. Discontinuation from Study Treatment

8.1.1. Temporary Interruption of Investigational Product

In some circumstances, patients may need to temporarily interrupt treatment as a result of AEs or abnormal laboratory values that may have an unclear relationship to investigational product. Except in cases of emergency, it is recommended that the investigator consult with Lilly (or its designee) before temporarily interrupting therapy for reasons other than those defined in [Table JAHV.7](#).

For the abnormal laboratory findings and clinical events (regardless of relatedness) listed in [Table JAHV.7](#), specific guidance is provided for temporarily interrupting treatment and when treatment may be restarted. Retest frequency and timing of follow-up laboratory tests to monitor the abnormal finding is at the discretion of the investigator. Investigational product that was temporarily interrupted because of an AE or abnormal laboratory value not specifically covered in [Table JAHV.7](#) may be restarted at the discretion of the investigator.

Table JAHV.7. Criteria for Temporary Interruption of Investigational Product

Hold Investigational Product if the Following Laboratory Test Results or Clinical Events Occur:	Investigational Product May be Resumed When:
WBC count <2000 cells/ μ L ($<2.00 \times 10^3/\mu$ L or <2.00 billion/L)	WBC count ≥ 3000 cells/ μ L ($\geq 3.00 \times 10^3/\mu$ L or ≥ 3.00 billion/L)
ANC <1000 cells/ μ L ($<1.00 \times 10^3/\mu$ L or <1.00 billion/L)	ANC ≥ 1500 cells/ μ L ($\geq 1.50 \times 10^3/\mu$ L or ≥ 1.50 billion/L)
Lymphocyte count <500 cells/ μ L ($<0.50 \times 10^3/\mu$ L or <0.50 billion/L)	Lymphocyte count ≥ 1000 cells/ μ L ($\geq 1.00 \times 10^3/\mu$ L or ≥ 1.00 billion/L)
Platelet count <75,000/ μ L ($<75 \times 10^3/\mu$ L or <75 billion/L)	Platelet count $\geq 100,000/\mu$ L ($\geq 100 \times 10^3/\mu$ L or ≥ 100 billion/L)
eGFR <40 mL/min/1.73 m ² (from serum creatinine) for patients with screening eGFR ≥ 60 mL/min/1.73 m ²	eGFR ≥ 50 mL/min/1.73 m ²
eGFR <30 mL/min/1.73 m ² (from serum creatinine) for patients with screening eGFR ≥ 40 to <60 mL/min/1.73 m ²	eGFR ≥ 40 mL/min/1.73 m ²
ALT or AST >5 x ULN	ALT and AST return to <2 x ULN, and IP is not considered to be the cause of enzyme elevation
Hemoglobin <8 g/dL (<80.0 g/L)	Hemoglobin ≥ 10 g/dL (≥ 100.0 g/L)
Symptomatic herpes zoster	All skin lesions have crusted and are resolving

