In exceptional circumstances, to ensure patient safety and with the sponsor's prior written approval, local laboratory testing may be conducted in lieu of central laboratory testing. The local laboratory must be qualified in accordance with local regulations. Clinically significant laboratory findings must be recorded as an AE in the AE eCRF.

For patients unable to access investigator sites, laboratory testing will be conducted at least every 8 weeks in the OLLI and DBW periods. The first collection should be 8 weeks from the patient's last collected central laboratory samples.

Failure to have labs collected within the described ranges above may result in patient termination from the study.

When collecting local labs, sites should store records from the labs including results, address, certification (College of American Pathologists/Clinical Laboratory Improvement Amendments [CAP/CLIA]) status, and reference ranges. The PI/Sub-I should sign and date review of local labs per normal process and follow-up with the patient as needed. Local labs may be sent to the patient as this is standard process in clinical care.

Note: Any results that are obtained from local laboratories will need to be retained by the investigator for their respective patients.

The laboratory measures listed below are the **minimum** required in order to monitor patient safety and determine temporary or permanent discontinuation of IP. Additionally, investigators should include any symptom-based laboratory testing based on their interactions with the patients. As stated in the protocol, investigators are responsible for monitoring the overall health of their patients.

The investigators should request the following laboratory analyses for these select parameters:

- WBC
- ANC
- Lymphocyte count
- Hemoglobin
- Platelet count
- ALT, AST, total bilirubin, INR
- ESR
- Urine pregnancy

These laboratory results will allow the investigators to follow both the temporary and permanent discontinuation criteria as provided in the protocol (Section 8.1.1 Temporary Interruption of Investigational Product and Section 8.1.2. Permanent Discontinuation from Investigational Product)

5. Documentation

a. Changes to study conduct

Changes to study conduct will be documented as the following:

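### Appendix 8's minimum local laboratory list omits serum creatinine/eGFR (and ALP), so it cannot support every hold and stop rule it is said to support (minor, patient safety)

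*Protocol*

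**What the plan says.** Protocol Appendix 8 covers exceptional circumstances such as a pandemic. Item 4 provides that, with prior written sponsor approval, "local laboratory testing may be conducted in lieu of central laboratory testing". For patients who cannot reach a site, "laboratory testing will be conducted at least every 8 weeks in the OLLI and DBW periods".

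The item then sets out the minimum tests needed for safety monitoring and for hold or stop decisions: WBC, ANC, lymphocytes, hemoglobin, platelets, a chemistry line reading "ALT, AST, total bilirubin, INR", ESR and urine pregnancy. It also asks for extra testing prompted by symptoms. It closes with the statement at issue, citing Sections 8.1.1 and 8.1.2: "These laboratory results will allow the investigators to follow both the temporary and permanent discontinuation criteria as provided in the protocol".

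Table JAHV.7 in Section 8.1.1, whose left column is headed "Hold Investigational Product if the Following Laboratory Test Results or Clinical Events Occur", has two eGFR rows. Each contains the wording "from serum creatinine) for patients with screening eGFR", followed by the screening band to which it applies. Section 8.1.2 lists seven liver conditions for considering permanent discontinuation; three of them use ALP.

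**The concern.** The appendix tells sites that a named set of results is enough to apply both sets of criteria. If an analyte that a rule depends on is absent, a site that follows the appendix exactly will believe it is applying a rule that it cannot apply.

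Renal function is where this matters most. The protocol itself ties renal function to dosing. Section 7.4 says "The baricitinib dose for patients will be reduced by 50% in those who have renal impairment" at baseline, the cut-off being eGFR below 60. After that, "The baricitinib dose for an individual patient will not change during the course of this study", and Section 8.1.2 has no eGFR criterion. The hold row in Table JAHV.7 is therefore the only rule with an eGFR threshold that operates once a child is on study. Item 3 of Appendix 8 lets drug supply continue without a full visit, including delivery to the home. A child could thus keep taking drug while the one renal safeguard goes unchecked.

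**Working it through.** No sample size, power or alpha figure is involved. The check matches each laboratory rule against the item 4 list, using the list alone.

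**Step 1: how many hold rules apply to a child.** Table JAHV.7 has 8 laboratory rows: WBC, ANC, lymphocytes, platelets, eGFR (two rows), ALT/AST and hemoglobin. The eGFR rows are mutually exclusive by screening value (60 or above; 40 to below 60). Exclusion criterion [42] in Section 6.2 bars screening eGFR below 40, so exactly one applies to each eligible child. Rules per child: 8 − 1 = 7.

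**Step 2: match to the list.**

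| Hold rule (Table JAHV.7) | Analyte on item 4 list? |
|---|---|
| WBC <2000 cells/µL | Yes |
| ANC <1000 cells/µL | Yes |
| Lymphocytes <500 cells/µL | Yes |
| Platelets <75,000/µL | Yes |
| Hemoglobin <8 g/dL | Yes |
| ALT or AST >5 x ULN | Yes |
| eGFR <40 (screening ≥60) or <30 (screening 40 to <60) | No |

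Covered: 6 of 7. Uncovered: 7 − 6 = 1. Counted by table row, this is 6 of 8.

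**Step 3: does anything else make creatinine routine?**
- Table JAHV.2, footnote v, puts eGFR in the scheduled clinical chemistry, but that central testing is what item 4 allows to be replaced.
- The repeat liver panel in Section 9.4.5 (ALT, AST, ALP, total and direct bilirubin, GGT, creatine kinase) has no creatinine.
- The hepatic tests in Appendix 4 have no creatinine.
- Symptom-led testing needs a symptom. The eGFR hold is a laboratory threshold with no symptom attached.

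**Step 4: Section 8.1.2.** The four hematology stops (WBC, ANC, lymphocytes, hemoglobin) and pregnancy all use listed tests. Of the seven liver conditions, four rest on ALT or AST, which are listed. The other three rest on ALP, which is not: ALP >3 x ULN judged hepatic and drug-related; ALP >2.5 x ULN with bilirubin >2 x ULN; and ALP >2.5 x ULN with symptoms. Against the list alone, 3 of 7 cannot be checked.

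These three differ once other routes are considered. A bilirubin of 2 x ULN or more triggers the Section 9.4.5 panel, which includes ALP. Symptoms could prompt an ALP test. An isolated ALP above 3 x ULN has no reflex route, because nothing on the list would prompt the measurement.

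**Step 5: after the change.** Adding creatinine with eGFR takes hold-rule coverage from 6 of 7 to 7 of 7. Adding ALP supplies the missing analyte for the remaining 3 liver conditions.

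**The case against.** The best defence is that the list is a floor. It is labelled a minimum, investigators remain responsible for overall monitoring, and symptom-led tests are requested. Use needs written sponsor approval, is case by case and ends when restrictions lift. Further sponsor guidance is promised. Missing data are to be recorded as protocol deviations, which suggests that scheduled chemistry is not simply cancelled. Under item 2, patients followed remotely in the open-label lead-in leave at Visit 9.

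All of this stands as a limit on size. It does not rescue the sentence, which says that these results are enough. The promised guidance is not in the documents, and recording a missing value afterwards does not detect a falling eGFR. The Visit 9 exit does not close the gap either, since it comes only at the end of the lead-in and item 4 expressly covers the double-blind withdrawal period too.

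A reader might infer more than the documents support:

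- *A child already on an eGFR hold could be restarted unchecked.* Section 8.1.1 leaves follow-up testing of the abnormal finding to the investigator, and restart requires the threshold to be met. A missing creatinine keeps that child off drug. The gap concerns detecting a new fall.
- *HBV DNA monitoring lapses as well.* Table JAHV.2, footnote t, and Appendix 2, footnote g, make scheduled testing mandatory for every enrolled hBcAb-positive patient. Nothing in Appendix 8 waives this.
- *Eosinophilia goes unmonitored.* It is one of several alternative accompanying features in two liver conditions, and it matters only once ALT/AST or ALP is raised. ANC and lymphocyte counts are already listed, so asking for eosinophils adds little.
- *Long off-site stretches lose a countable number of creatinine results.* Such a count only restates that one added test per draw gives one result per draw. It says nothing about risk.

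**Conclusion.** The sufficiency statement is wrong as written, and the point is minor. For every eligible child, 1 of the 7 applicable laboratory hold rules (eGFR) cannot be applied from the item 4 list. Three of the 7 Section 8.1.2 liver conditions lack their analyte, and one of those (isolated ALP) also has no reflex route. The creatinine gap is the main finding and would stand without ALP; the liver conditions are ones that should prompt considering discontinuation after consultation, not automatic stops.

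The conclusion assumes that a site draws the stated minimum and no more, and that unseen sponsor guidance does not already add creatinine. The documents give neither the number of children managed under this provision nor any rate of eGFR decline. They therefore do not support a claim that harm is likely or that many children are exposed. Nor is there any consequence for the efficacy analysis, power or alpha. This is an inconsistency between Appendix 8 and Section 8.1, with a patient-safety consequence that is cheap to remove.

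**What to change.** Add serum creatinine and ALP to the item 4 list, on the same local sample as ALT, AST and total bilirubin. Require eGFR to be calculated from that creatinine with the protocol's formula (Bedside Schwartz 2009, or the Japanese Society for Pediatric Nephrology formula in Japan), using the most recent body measurement the formula needs.

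If the list is left alone, narrow the closing sentence to what it covers: the WBC, ANC, lymphocyte, platelet and hemoglobin rules, the ALT/AST rules including those with bilirubin or INR, and pregnancy. That corrects the statement but leaves renal monitoring of off-site children to discretion, so adding the analytes is preferable.

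The cost is two analytes on a draw already required, a recent body measurement, and a site letter or short protocol clarification. The 8-week interval is unchanged.

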5.1 Overall Design

...

- a Staggered approach to enrollment by age group (12 to <18 years, ~~6~~ 9 to <12 years, 6 to <9 years, 2 to <6 years) will be implemented with older groups completing the safety/PK assessment period before younger groups are enrolled.
- b Once the PK and safety profiles for an age group are confirmed, subsequent patients in that age group may enroll directly into the OLLI period. If the comparability assessment in the safety/PK period for an age group is inconsistent with baricitinib 4-mg exposures in adults with RA such that baricitinib dosage for the age group needs to be adjusted, the patients on the inconsistent dosage will discontinue the study and may enter the separate OLE study (JAHX).
- c Patients who experience a disease flare during the DBW period will discontinue the study and may proceed directly to the separate OLE study (JAHX).

